Randomization will be stratified by institution and anatomic lead location (**Table 4**) in a 1:1 ratio and in randomly chosen block sizes. Randomization lists for each enrolling center will be created by the Cleveland Clinic. Treatment group assignment will be conveyed to the enrolling sites via the same secure web-based system (RedCap) used to collect and collate all post-intervention endpoints (see “Data Collection” paragraph below). Stimulators are capable of programming to either (1) pass electrical current; or, (2) not pass electrical current. Importantly, these 2 modes (active and sham) are indistinguishable in appearance, and therefore investigators, subjects, and all clinical staff will be masked to treatment group assignment, with the only exception being the unmasked individual who programs the stimulator (and will not have direct contact with the subject). The unmasked personnel will have access to the randomization list on RedCap, program the stimulator appropriately (sham vs. active), and provide the investigator interacting with the study subject with the device without indicating the treatment group.

Subjects will be informed that often during postoperative active treatment with electrical current patients do not always have the sensations experienced during preoperative lead placement and once proper placement is confirmed with comfortable sensations, therapeutic levels of stimulation may be delivered sub-threshold (below the intensity required for sensation and still provide relief, which is factual/accurate). ***This protocol will ensure a randomized, double/triple-masked, sham/placebo-controlled trial.*** For the feasibility study (UG3), unmasking will occur 2 weeks following surgery to allow for protocol revisions, as necessary (“double masked” during data collection). In contrast, for the definitive pragmatic clinical trial (UH3) unmasking will not occur until statistical analysis for the entire investigation is complete (termed “triple masked”).

Intraoperative course. The primary surgical anesthetic will be a general anesthetic, spinal anesthetic (bupivacaine 0.5%) or exclusively the preoperative single-injection peripheral nerve block. Anesthetics that are also analgesics such as ketamine will not be used: the only permitted analgesic will be intravenous fentanyl, which will be minimal since all subjects will receive a single-injection peripheral nerve block immediately prior to surgery.

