Postoperative course. Within the recovery room following surgery, the stimulators will be attached to the leads and activated, followed by end point assessment. Subjects who had a spinal anesthetic will have end points recorded following spinal resolution. Operating and recovery room pharmacologic analgesic requirements will be recorded.

Post-hospital course. Prior to discharge, subjects and their caretakers will be provided with verbal and written stimulator/lead instructions and the telephone and pager numbers of a local investigator available at all times. Subjects will be discharged home with their leads *in situ*, and contacted every-other day by a healthcare provider until lead removal. Subjects will be also be discharged with a prescription for immediate-release oral oxycodone (5 mg tablets taken for breakthrough pain).

Therefore, *all* patients of this study—regardless of the treatment arm they are randomized to—will continue to receive current usual and customary analgesia. Subjects will be contacted by telephone for end point collection. Lead removal will occur on postoperative day 14 (+/- 2 days) by healthcare providers. If the lead is removed following Day 14, the stimulator will be turned off on Day 14 and removed subsequently. Similar to perineural catheters,¹³⁵ this procedure encompasses simply removing the occlusive dressing and gently pulling on the lead. Following study completion, the results will be mailed electronically or by the United States Postal Service to all enrolled subjects in written form using non-technical language.

Outcome measurements (end points). We have selected outcome measures that have established reliability and validity, with minimal inter-rater discordance, and are recommended for pain-related clinical trials by the World Health Organization and the Initiative on Methods, Measurement, and Pain Assessment in Clinical Trials (IMMPACT) consensus statement.¹³⁶ Importantly, nearly all outcome measures are common data elements from the National Institute of Neurological Disorders and Stroke (NINDS).¹³⁷ End points (Table 2) will be evaluated at baseline (prior to surgery on postoperative day 0), during the treatment period (postoperative days 1-14); and the follow-up period (postoperative day 15 and months 1, 4, and 12).

Table 2. Summary of post-enrollment assessments (color added for clarity)

Time Point:	Postoperative Days								Postoperative Months		
	0	1	2	3	4	7	11	15	1	4	12

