Data collection. Much of the surgical data from the day of surgery will be extracted from electronic health records to leverage data collection that occurs in health care delivery rather than requiring independent research data collection. Subject demographic, surgical and percutaneous PNS administration data will be uploaded from each enrolling center via the Internet to a secure,¹⁴⁴ password-protected, encrypted central server (RedCap, Department of Outcomes Research, Cleveland Clinic, Cleveland, Ohio).¹⁴⁵ All data collection following the day of enrollment (postoperative day 0)—regardless of enrolling center—will be collected by telephone from the University of California San Diego. Staff masked to treatment group assignment will perform all assessments.

UG3 Milestones. The 2-year UG3 feasibility period has explicit milestones (**Table 3**, following page) that are feasible, quantifiable, and scientifically justified to allow an assessment of progress. **Each of the items listed in Table 3 and the following outline is considered a milestone and must be completed in order to proceed to the 4-year UH3 definitive, pragmatic clinical trial.**

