Register study and update on clinicaltrials.gov					•	•
Subject enrollment (following IRB approval)					•	
Data collection, University California San Diego (Day 1 to Month 3)				•	•	
Quality assurance					•	•
Address any ethical, human subject safety and oversight issues					•	•
Assess adequacy of protocol, data-entry platform, and study sites					•	•
Replace any study sites, if necessary						•
Data cleaning and statistical analysis						•
Revise pragmatic clinical trial (UH3) statistical section, as necessary						•
Revise protocol for pragmatic clinical trial (UH3), as necessary						•
If necessary, revise budget for pragmatic clinical trial						•
IRB revisions at enrolling centers and oversight agencies, if needed						•
Manuscript preparation: protocol description						•
Upload results to ClinicalTrials.gov						•
Final UG3 report to funding and oversight agencies						•

CRADA: Cooperative Research and Development Agreement

Regulatory Review and Approval Process. Of note, the entire first year of the funding period is currently designated for this purpose due to the often-prolonged period of time required for regulatory

review and approval. However, enrollment may commence sooner if the regulatory process requires less than 1 year. This is probable since the stimulation system used in the proposed investigation is already cleared for use in treating acute pain, and therefore US FDA investigational device exemption approval is not needed and the proposed use in this study is on label. The final protocol will be formatted and then submitted to all enrolling site IRBs and the funding agency's oversight committee (e.g., U.S. Army Medical Research and Materiel Command Human Research Protection Office). The DSMB will be initiated which will design the DSMB charter describing role, reporting procedures, and meeting protocol. A Medical Monitor (DSMB Chair, "subject advocate") will receive monthly reports prepared by the Principal Investigator (reviews project accomplishments, issues, problems, upcoming goals, adverse events, protocol deviations, etc.). DSMB will occur at a minimum of very 6 months, or more often if specified by the DSMB charter. The DSMB will review progress and recommends modification, continuation, or termination:

- Approval of the trial protocol before enrollment
- Review data in order to determine efficacy, futility, and safety, and to determine continuation
- Review data quality and data integrity

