enrolling site, with the case report forms faxed to the Principal Investigator at the University California San Diego using a secure fax machine in a locked office to protect personal health information. All data collection following the day of surgery will occur by telephone from the University of California San Diego, which will then enter all data to the database. For the UG3 feasibility study, the final data collection point for each subject will be at 4 months following surgery (the 12-month time point will be used for the definitive UH3 pragmatic clinical trial). Quality assurance will be ongoing by the University of California San Diego, which will monitor data for sources of error and report to the Medical Monitor (DSMB Chair) with written monthly reports. Each enrolling center will be expected to enroll at least 1 subject for each of the 3 possible lead locations (e.g., brachial plexus trunks) in each of the first two quarters of the 2nd year of the funding period. Combined, the 7 centers will enroll a total of 64 subjects as part of the feasibility study.

Preparation for the UH3 Clinical Trial. If one or more centers fails to enroll their designated subjects—for whatever reason(s)—other centers will make up this enrollment with coordination by the Principal Investigator. The 64-subject feasibility study will enable evaluation of the study intervention, protocol, case report forms, outcome measures, data-entry platform, Research Coordinators, Site Directors, and study oversight. Any changes deemed necessary by the Principal Investigator in concert with the DSMB, funding agency, Steering Committee, Site Directors and NIH-DoD-VA Pain Management Collaboratory Coordinating Center will be made to any aspect of the study design (such as the outcome measures or informed consent forms), including replacing any enrolling center that fails to demonstrate the ability to adequately enroll and execute the protocol. The data from the first 64 subjects will be cleaned by University of California San Diego and a statistical analysis performed by the study statistician ([name]) at the Department of Outcomes Research (Cleveland Clinic).

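### UG3 is to be unmasked 2 weeks after surgery although its self-reported telephone outcomes run to month 4, and the plan does not say who is unmasked

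*Combined protocol and SAP*

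**What the plan says.** All the relevant text is in section 9 of the combined protocol and SAP.

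- **Before unmasking.** Treatment group assignment (randomization): "investigators, subjects, and all clinical staff will be masked to treatment group assignment". The only exception is the person who programs the stimulator.
- **Time of unmasking.** The same paragraph: "For the feasibility study (UG3), unmasking will occur 2 weeks following surgery to allow for protocol revisions". The sentence goes on to describe the pilot as double masked while data are collected. For UH3, by contrast, the paragraph defers unmasking until the whole analysis is finished.
- **Visits.** Outcome measurements and Table 2 place end points at baseline, in the treatment period, and in "the follow-up period (postoperative day 15 and months 1, 4, and 12".
- **End of pilot collection.** The Enrollment paragraph under UG3 Milestones: "the final data collection point for each subject will be at 4 months following surgery". The Table 3 timeline differs: "Data collection, University California San Diego (Day 1 to Month 3".
- **How outcomes are collected.** The same Enrollment paragraph: "All data collection following the day of surgery will occur by telephone from the University of California San Diego".
- **Who assesses.** Data collection: "Staff masked to treatment group assignment will perform all assessments". No exception is given for UG3 or for calls after the second week.

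**The concern.** The late pilot outcomes are subjective: pain ratings, interference, quality of life and recalled opioid use, all given over the telephone in a sham-controlled device study. A subject who knows that the stimulator delivered no current, or an interviewer who knows it, can shift such answers. Masking exists to prevent this, and the plan ends it before the last three pilot visits while still calling the pilot double masked.

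What is at stake is the credibility of the pilot's later results. The planning-phase methods include tests of functioning, chronic pain and quality of life. The Planning Phase sample size paragraph expects the pilot to inform the effect and variability of each outcome in the larger trial. The pilot may also prompt changes to the outcome measures, and its results are to be published and posted. A reader told that these data are double masked would be misled about the later visits. Table 2 schedules its one masking assessment on day 1, so nothing would record what subjects knew or believed later on.

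**Working it through.** No sample size, power or significance level depends on this point. The check compares the unmasking time with the visit schedule.

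**Inputs.** Unmasking at 2 weeks, about day 14 (Treatment group assignment). Visits on days 0, 1, 2, 3, 4, 7, 11 and 15 and at months 1, 4 and 12 (Table 2). UG3 stops at month 4 (Enrollment, under UG3 Milestones).

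**Visits in UG3.** Dropping month 12 leaves 8 + 2 = 10 time points. Seven (days 0 to 11) come before day 14. Three (day 15, months 1 and 4) come after it.

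| Outcome | Post-baseline UG3 visits | After 2 weeks | If unmasking follows the day 15 call |
|---|---|---|---|
| Brief Pain Inventory | days 3, 7, 15; months 1, 4 | 3 of 5 | 2 of 5 |
| DVPRS | days 3, 7, 15; months 1, 4 | 3 of 5 | 2 of 5 |
| WHOQoL-BREF | months 1, 4 | 2 of 2 | 2 of 2 |
| NRS pain, opioid use | 10 − 1 = 9 visits | 3 of 9 | 2 of 9 |

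**Month 3 or month 4.** Table 3 and the Enrollment paragraph disagree on the last call. If a month 3 call replaced the month 4 call, the counts would not change. If month 4 were simply dropped, the Brief Pain Inventory and DVPRS would have 2 of 4 visits after unmasking and WHOQoL-BREF 1 of 1. The problem remains either way.

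**Who is unmasked.** The sentence does not say, so each reading has to be tried.

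1. *Everyone who was masked.* Subjects, investigators and staff learn the allocation. Then neither the description of the pilot as double masked during collection nor the promise of masked assessors holds after week 2.
2. *Subjects and site investigators, but not the telephone assessors.* The promise about assessors can hold literally. Subjects still self-report knowing their arm, and may reveal it on the call.
3. *Only those revising the protocol.* Later outcomes can stay masked, but the plan would have to say so. The lead center that makes the calls is also where the Principal Investigator receives case report forms and where pilot data are cleaned, so the separation needs stating.
4. *Two weeks after the last subject's surgery.* Subjects enrolled late would still give month 1 and month 4 data after unmasking.

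Every reading needs a change or an addition to the text.

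**What is not touched.** The primary end points cover days 0-7, and 7 is less than 14. The UH3 sample size paragraphs use only 7-day opioid consumption and 7-day pain. UH3 has its own, later unmasking rule.

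**The case against.** The early unmasking is a disclosed choice. It is stated openly, given a reason, and contrasted with UH3. The double-masked label may be meant only to distinguish the pilot from a trial in which the statistician is masked too. The stated purpose fits the people who revise the protocol at least as well as the patients. If the callers are simply not told, the unmasking sentence and the promise of masked assessors can both stand. Day 15 is also uncertain: Table 2 has no day 14 visit, so the day 15 call may be the intended 2-week contact.

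Most of this stands. It means the defect is an unspecified scope of unmasking, not a proven contradiction about the assessors, and it is why the count is given as 3 of 5 or 2 of 5. It does not remove the problem, because nothing in the plan says that subjects or callers stay masked.

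A reader might infer three stronger things that the documents do not support:

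- **That the pilot's main estimates, or UH3, are compromised.** UG3 Specific Aim 2 concerns pain and opioid consumption, and the end points that drive UH3 sizing are collected before unmasking. Hypothesis 4 is set at 6 and 12 months, so a pilot ending at month 4 has no estimate at those times to bias.
- **That allocation concealment fails.** With 7 sites and 3 lead locations there are 21 strata, averaging 64/21 ≈ 3 subjects, so disclosed assignments might seem to help a site guess the next one. That presumes subject-by-subject disclosure to enrolling sites, which is not stated. Block sizes are chosen at random, and allocation follows lead insertion and the start of surgery.
- **That subjects will certainly be told their arm.** This is the natural reading but not an explicit statement.

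On cost, pilot enrollment fills the first 6 months of year 2, so the last month 4 call falls at about month 6 + 4 = 10. Waiting for it before any by-arm review would leave about 2 months for revision and resubmission. That is a fair objection to a blanket delay, and the fix allows for it.

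**Conclusion.** The point holds as a gap in the pilot's masking rules. As written, the 2-week unmasking, collection to month 4 and the double-masked label do not fit together, and no other section reconciles them. If subjects or callers learn the allocation, 3 of 5 post-baseline Brief Pain Inventory and DVPRS visits (2 of 5 if unmasking follows the day 15 call), both WHOQoL-BREF visits, and the pain and opioid values at those visits are open to expectation bias. The pilot would then have no masked post-baseline quality-of-life data.

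The conclusion assumes that unmasking reaches subjects or telephone assessors and is timed from each subject's own surgery. The documents give no basis for estimating the size of any bias, and none is claimed. The correction is worth making, but the point does not threaten the days 0-7 primary end points or the definitive trial.

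**What to change.** Amend Treatment group assignment (randomization) to state who is unmasked in UG3 and when:

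- Subjects and telephone assessors stay masked until each subject's last UG3 call.
- Earlier unmasking is limited to those who need it for protocol revision, for example the statistician and the DSMB. By-arm summaries can go to the revising team once pilot enrollment closes. These should be pooled over sites, since strata of about 3 subjects could reveal individuals.
- The last UG3 call is given the same month in Table 3 and in the Enrollment paragraph.

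If the sponsor prefers to unmask subjects or assessors earlier, it should report the later UG3 outcomes as unmasked, drop the double-masked description for those visits, and add the exception to the Data collection paragraph.

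The cost is a wording change and a rule on who sees what at the lead center. The wider team learns individual allocation later. Revision need not wait for the last call, because it can proceed on summaries from the end of enrollment, and it does not require subjects or callers to know individual assignments.

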In concert with the NIH-DoD-VA Pain Management Collaboratory Coordinating Center, the statistical section for the subsequent UH3 pragmatic clinical trial will be revised to reflect the **estimated treatment effect** and treatment group means. For the initial submission, we have estimated the probable maximum sample size for budgeting and planning purposes; but, the results of the initial feasibility study will most-likely decrease the definitive UH3 pragmatic trial required sample size. The statistical section and budget will be revised to reflect any changes. Any revisions to the protocol or informed consent forms will be submitted to the DSMB, individual center IRBs and funding center's oversight body. A manuscript with the results of the pilot study will be prepared and submitted with the results concurrently uploaded to ClinicalTrials.gov. Lastly, a final UG3 period report will be prepared for the funding and oversight agencies.

UG3 Planning Phase Specific Aims. The investigation described above will accomplish the two Specific Aims of the UG3 Planning Phase:

Specific Aim 1 (UG3): To determine the **feasibility** and **optimize** the protocol of the Implementation Phase (UH3) multicenter clinical trial that will compare percutaneous PNS with usual and customary opioid-based analgesia following moderate-to-severely painful ambulatory surgery.

Specific Aim 2 (UG3): To **estimate** the **treatment effect** of percutaneous PNS on pain and opioid consumption following moderate-to-severely painful ambulatory surgery compared with usual and customary opioid-based analgesia. This will allow determination of the required **sample size** of the definitive multicenter clinical trial of the Implementation Phase (UH3).

UH3 Implementation Phase

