Planning Phase sample size considerations. The sample size for the planning phase of 64 patients will be sufficient to estimate the treatment effects of interest with moderate precision, i.e., a confidence interval width of roughly 1.1 standard deviations for each outcome measure. Confidence interval width for a standard deviation estimate will be 0.70 standard deviations. The planning phase will be sufficient to use in estimating the expected treatment effect and standard deviation for each outcome for the larger trial.

UH3 Implementation Phase. Statistical methods for the UH3 Implementation Phase will follow very closely the methods described for the UG3 Planning Phase. The main difference is that UH3 Implementation Phase will have sufficient data to conduct the subgroup analyses and also considerably more power to assess the treatment effects of interest.

Another substantive difference from the planning phase is that in the full trial we will conduct interim analyses at each 25% of the planned enrollment using a group sequential method with gamma spending function and gamma parameter of -4 (quite conservative) for efficacy and 0 (moderately aggressive) for futility (**Figure 14**). The probability of crossing a boundary for either efficacy (mainly) or futility at the first through fourth looks would be 0.10, 0.42, 0.80 and 1.0, respectively, assuming the alternative hypotheses were true.

Figure 14. Stopping boundaries for 1-tailed tests for superiority for either pain score or opioid consumption. Blue region indicates superiority (reduced opioid consumption or pain score) and pink region indicates futility (lack of superiority). Z-statistic represents strength of evidence against the null hypothesis, either ratio of means or difference in means divided by standard error.

Missing outcomes data will be summarized along with the etiology of the absence. | While very little outcomes data is expected to be missing,

analyses will be intention to treat, and imputation of missing data using methods such as multiple imputation and last observation carried forward will therefore be utilized, based on the situation. In a conservative analysis imputation will involve the conservative approach of assigning the worst observed outcome to patients in intervention groups and best observed outcomes to those in control.

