Throughout, the significance level will be 0.05 for each hypothesis. SAS statistical software (Cary, NC) will be used for all analyses, and East 6.0 (Cytel, Inc. Cambridge, MA) for interim monitoring and sample size calculations.

UH3 Implementation Phase sample size considerations. Sample size parameters for the implementation phase will be derived from estimates in the planning phase. The sample size calculations below are conservative in that we observed a coefficient of variation for opioid consumption observed in our preliminary data of 0.48, substantially better than the assumed 0.65. It is thus quite possible that the actual sample size for the implementation phase will be smaller.

Sample size for the full trial will be chosen to allow an overall 90% power at the 0.025 significance level (since 1-tailed tests) to claim the intervention more effective than the control on postoperative opioid requirements and pain as measured by NRS pain score. In our joint hypothesis testing on these two outcomes, we power the study to have overall 90% power to detect superiority on either

outcome and at least noninferiority on both. We assume a coefficient of variation of 1.0 for opioid consumption and a standard deviation of 2 for pain score.

Power for the joint hypothesis testing will be driven by superiority tests since superiority is needed for at least 1 of the 2 outcomes. For cumulative opioid consumption through POD 3 our previous data had a coefficient of variation (CV) of 46% (mean (SD) of 28 (13) mg). Conservatively assuming a coefficient of variation of 75% through 7 days,¹⁸³ with a total N=528 we would have 90% power to detect a relative reduction of 20% in mean opioid consumption at the overall 0.025 significance level (0.0125 for each of the two 1-tailed tests for superiority), adjusting for interim analyses (N=448 before adjustment for interim analyses).

This sample size will yield high power (>0.95%) to detect superiority based on the intervention group having 1 point or more better than the control group on NRS pain score within the first 7 days, assuming a standard deviation of 2 points for mean of the “average” pain score for each patient.

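### The UH3 sample size is tied to the treatment effect estimated in a 64-patient pilot, with no fixed target effect, minimum N or re-sizing rule, so the 90% power is not protected

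*Combined protocol and SAP*

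**What the plan says.** Everything cited is in the combined protocol and SAP.

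- **UG3 Specific Aim 2** (section 6, repeated twice in section 9) says that estimating the pilot's treatment effect will allow the UH3 sample size to be determined.
- **Section 9, Preparation for the UH3 Clinical Trial:** "the statistical section for the subsequent UH3 pragmatic clinical trial will be revised to reflect the" pilot's effect estimate and arm means. On the current N, "we have estimated the probable maximum sample size for budgeting and planning purposes", and the plan then expects that "the results of the initial feasibility study will most-likely decrease the definitive UH3 pragmatic trial required sample size".
- **Section 9, Statistical Plan and Data Analysis:** the planning phase will focus on the confidence interval for the effects and on outcome variability, and these are to feed the design of the full trial.
- **Section 9, Planning Phase sample size considerations:** "The planning phase will be sufficient to use in estimating the expected treatment effect and standard deviation for each outcome for the larger trial".
- **Section 9, UH3 Implementation Phase sample size considerations:** "Sample size parameters for the implementation phase will be derived from estimates in the planning phase". The same section gives the present calculation: N=528 (448 before interim adjustment) for 90% power to detect a 20% opioid reduction. It also says N may fall because the CV in preliminary data (0.48) was below an assumed 0.65.

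No section keeps the 20% reduction or the 1-point pain difference as a target that survives the revision. None sets a minimum N, shrinks the pilot estimate or gives a re-sizing formula.

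**The concern.** A pilot of this size can give a usable estimate of variability, but its estimate of the effect is noisy. If that estimate replaces the effect to be detected, the error is one-sided in its consequences. A pilot that overstates the effect by chance leads to a smaller UH3. A pilot that understates it leaves N at the planned maximum, because the plan treats the current N as a ceiling. UH3 would then be underpowered in just those cases where the pilot misled, and a real 20% opioid reduction could be missed.

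**Working it through.** **Inputs from the plan.** Pilot: "Combined, the 7 centers will enroll a total of 64 subjects as part of the feasibility study", allocated "in a 1:1 ratio and in randomly chosen block sizes", so 32 per arm. One-sided alpha 0.0125 per outcome, power 90%, opioid ratio 0.80, CV 0.75, analysis on the log scale, pain SD 2. Four looks, with gamma -4 for efficacy and gamma 0 for futility. The plan states no dropout inflation, so none is used.

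**Step 1: reproduce the plan's N.**
- Log-scale SD = sqrt(ln(1 + 0.75²)) = 0.668.
- Effect = |ln 0.80| = 0.2231, or 0.2231/0.668 = 0.334 SD.
- N = 4 × (2.241 + 1.282)² / 0.334² ≈ 445, or 446 with a t correction (stated 448). Power at 448 is 0.902.
- The stated boundaries with non-binding futility inflate N by 1.182, giving 527-530 (stated 528).
- The section also mentions CVs of 0.65 and 1.0. These give 352 and 692, so only 0.75 matches the stated N.

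**Step 2: precision of the pilot effect.**
- SE = sqrt(2/32) = 0.25 SD, or 0.668 × 0.25 = 0.167 on the log scale.
- The 95% interval is 2 × 1.96 × 0.25 = 0.98 SD wide (the plan says roughly 1.1), about three times the 0.334 SD effect.
- If the true ratio is 0.80, 95% of pilot estimates fall between about 0.58 and 1.11, and 9% point the wrong way.
- A pilot at the favourable quartile shows a ratio of 0.715. The formula then gives N ≈ 196 before interim adjustment, and true power is Φ(0.334 × sqrt(196)/2 − 2.241) ≈ 0.54.

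**Step 3: re-size on the point estimate.** I simulated 1,000,000 pilots with a true ratio of 0.80. N was recomputed from each pilot effect and capped at 448 on the fixed-design scale (528 with looks). Wrong-direction pilots were left at the cap. Power is for opioid superiority.

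| Quantity (CV 0.75) | Result |
|---|---|
| Pilots in which N is cut | 50% |
| Median true power when N is cut | 54% |
| Mean power | 72% |
| Median power | about 90% |
| Chance of power below 80% | 42% |
| Chance of power below 50% | 22% |

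Under the same rule, mean power is 81% at CV 0.48, 76% at CV 0.65 and 60% at CV 1.0. With N left at the planned size, power at CV 0.65 and 1.0 is 96% and 72%.

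**Step 4: other rules, CV 0.75.**

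| Rule | Mean power |
|---|---|
| Cap; wrong-direction pilots counted as no trial | 64% |
| Cap; such pilots excluded | 71% |
| No cap; such pilots excluded | 74% |
| No cap, wrong-direction pilots given full power; or cap with a floor of N=200 | 77% |
| Cap; sized on one-sided 80% lower bound | about 85% |
| Cap; sized on one-sided 90% lower bound | about 88% |

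**Step 5: joint primary rule** (superior on at least one outcome, noninferior on both), re-sized as in Step 3. The correlation between outcomes is an assumption, varied from 0 to 0.5.

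| True pain benefit | Mean power after re-sizing | Power at unchanged N |
|---|---|---|
| None | about 72% | 90% |
| 0.5 point | 77-81% | 93-97% |
| 1 point | 92-94% | over 99% |

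**Step 6: update only the SD from the pilot, keeping the 20% target.** Mean power is about 89% uncapped or 87% capped, with about a 9% chance of power below 80%.

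**The case against.** The strongest reply is that the plan never says the point estimate will be plugged into the formula. The Statistical Plan names the confidence interval and the variability as design inputs, and sizing on a lower bound loses much less power. This stands: 72% is the result of one permitted rule, and a reader should not infer that it is what the plan itself produces.

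A second reply is that the plan's overall 90% refers to the joint claim. This also stands. One might infer that the 90% fails whenever N is re-sized this way, but with a true 1-point pain benefit joint power is still 92-94%. The loss occurs when the pain benefit is absent or modest. That case matters, because section 9 describes the aim as cutting opioid use without a concurrent increase in pain.

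Third, the sentence expecting a smaller N does not name the effect as the cause, and the only specific reason given elsewhere is a lower CV. That sentence alone does not show that the effect will drive the cut. The link comes from the sentence before it, from Aim 2, and from the statement that the pilot suffices for "estimating the expected treatment effect and standard deviation for each outcome for the larger trial".

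Finally, the revision is made in concert with the Coordinating Center, and protocol changes go to the DSMB, the IRBs and the funder's oversight body. It is not automatic, but none of these bodies is given a criterion to apply.

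**Conclusion.** The concern holds as a gap in the design rules. The plan links UH3 sizing to a pilot effect whose standard error (0.25 SD) is three quarters of the effect to be detected (0.33 SD), expects N to fall, and sets no safeguard. For a true 20% opioid reduction at CV 0.75, every plug-in rule tried gives mean power for opioid superiority of 64-77%, and the rule closest to the text gives 72%. Lower-bound sizing gives 85-88%. These are averages: median power under the 72% rule is about 90%, and the shortfall comes from pilots that overestimate the effect. Under the joint rule the 90% is lost on average unless the pain benefit is also large. All these figures rest on re-sizing rules assumed here, because the plan states none.

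**What to change.** State that the effects to detect in UH3 stay at the values already in the sample size section: a 20% relative opioid reduction and 1 NRS point. Use the pilot only for the SD or CV, the missing-data rate and the recruitment rate. Make the following agree with this: Aim 2 wherever it appears (sections 6 and 9), Preparation for the UH3 Clinical Trial, the opening of the Statistical Plan, and both sample size subsections. In the UH3 subsection, also settle which CV (0.65, 0.75 or 1.0) is the planning value.

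If the sponsor prefers to let the pilot effect influence N, the plan should give the exact rule and a minimum N, with the resulting power under the joint primary rule.

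The cost is wording, plus giving up a possible saving in N after a large pilot effect. The 528 patients are already in the enrolment milestones (192 + 192 + 144). N can still fall if the CV proves lower, and the interim efficacy looks already allow early stopping if the effect is large.
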